8.4.2 Definition of Serious Adverse Events (SAE)

An adverse event (AE) or suspected adverse reaction is considered "serious" if, in the view of either the investigator or sponsor, it results in any of the following outcomes: death, a life-threatening adverse event, inpatient hospitalization or prolongation of existing hospitalization, or a persistent or significant incapacity or substantial disruption of the ability to conduct normal life functions. Important medical events that may not result in death, be life-threatening, or require hospitalization may be considered serious when, based upon appropriate medical judgment, they may jeopardize the participant and may require medical or surgical intervention to prevent one of the outcomes listed in this definition. Examples of such medical events include cardiac arrhythmia requiring intensive treatment in an emergency room or at home, or pancreatitis / kidney stones that do not result in inpatient hospitalization.

8.4.3 Classification of an Adverse Event

8.4.3.1 Severity of Event

For adverse events (AEs) not included in the protocol defined grading system, the following guidelines will be used to describe severity.

- Mild – Events require minimal or no treatment and do not interfere with the participant's daily activities.
- Moderate – Events result in a low level of inconvenience or concern with the therapeutic measures. Moderate events may cause some interference with functioning.

Abbreviated Title: Tolerability and efficacy of ketogenic diet in Parkinson’s Disease

Version Date: 04/19/2021

- Severe – Events interrupt a participant’s usual daily activity and may require systemic drug therapy or other treatment. Severe events are usually potentially life-threatening or incapacitating. Of note, the term “severe” does not necessarily equate to “serious”.]

Serious adverse events associated with ketogenic diet are rare and reported predominantly in pediatric epilepsy population with different comorbidities and varying neurodevelopmental impairment, thus are not directly applicable to the adult population with Parkinson’s disease. Potential risks associated with ketogenic diet include dehydration related to natriuresis, electrolyte depletion, metabolic acidosis, vomiting, and elevated cholesterol and lipoprotein levels. Adverse events associated with these risks are not defined in frequency. Three pilot studies of ketogenic diet in Parkinson’s Disease did not report any serious adverse events.

As a preventative measure, PD patients with cardiovascular and other major comorbidities will be excluded from the study, and EKG will be performed at admission baseline. Daily electrolyte testing will occur in all participants on study days 2-5, and daily clinical assessment for volume status will occur by metabolic unit staff and AI with maintaining blinding as possible in the absence of adverse events. Reporting of events such as vomiting or other ketogenic diet induction symptoms will occur to metabolic unit staff and relayed to study PI (not involved in rating) and independent medical monitor (IMM), except when medically necessary for unblinding to occur immediately (i.e. to provide emergent medical care). Baseline and end of study lipid panel will be measured and results made available to participants, with medical counseling to be provided in debriefing session on further checking outpatient with primary care physician if elevated or showing an upward trend.

Relationship to Study Intervention

All adverse events (Aes) must have their relationship to study intervention assessed by the investigator who examines and evaluates the participant based on temporal relationship and his/her clinical judgment. The degree of certainty about causality will be graded using the categories below. In a clinical trial, the study product must always be suspect.

- Related – The AE is known to occur with the study intervention, there is a reasonable possibility that the study intervention caused the AE, or there is a temporal relationship between the study intervention and event. Reasonable possibility means that there is evidence to suggest a causal relationship between the study intervention and the AE.
- Not Related – There is not a reasonable possibility that the administration of the study intervention caused the event, there is no temporal relationship between the study intervention and event onset, or an alternate etiology has been established.

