All testing to be done by AI, at a certain scheduled time daily or specified testing schedule with respect to last meal and dopaminergic medications or others potentially modulating neuromuscular system (see Table 2 description for list). If patient has DBS, the settings will not be adjusted unless there is the impression of study investigators including PI who are movement disorders specialists that a significant motor complication has occurred during the intervention that might be improved by DBS adjustment. For

Abbreviated Title: Tolerability and efficacy of ketogenic diet in Parkinson's Disease**Version Date:** 04/19/2021

example, dyskinesia has been reported in prior ketogenic PD trial (Phillips et al, 2018) and could be improved by reducing DBS stimulation. For more details on adverse events please refer to Sections 9.5-9.6.

Table 2 – flowchart / schedule of testing

Care will be taken to minimize participants' test/retest variability from psychotropic medications. Accordingly, medications from the following classes will be taken up to the night prior to testing (held for testing): anticholinergics, NMDA antagonists, dopamine blocking agents, muscle relaxants, anticonvulsants, GABA agonists. Tests will occur in the same order; and care will be taken to control timing of AM dopaminergic dose in relation to testing, providing instruction for participants to take their dopaminergic medications at a set 30 min prior to breakfast. Morning dopaminergic medications will be taken in the overnight fasting state to minimize group differences in pharmacokinetics related to diet, as outlined in section 4.1 above. For each participant, testing will be done in a single session lasting approximately 1.5-2 hours, and time from dopaminergic medication dose to end of testing will be around 2-3 hours. No changes will be made to dopaminergic medication prescription, unless clinical emergency as per credentialed clinician assessment. If participant's levodopa or agonist dose interval requires repeat dose during testing, we will make no changes but maintain the same dose schedule throughout the testing days 1-7 and week 3.

Test, meal, medication	Duration	Approx. time from DA Rx (hr:min)
Fasting BOHB (days 1-7, week 3) and plasma dopamine** (days 1-3 only)	(as per CC, ~7AM)	~12 hours
Dopaminergic medications, L-DA / DA	(fasting) 7:30-8AM	~12-13 hours
Breakfast (pureed shake)	(~8-8:30)	~30 min
TUG	20 min	~1 hr

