(rsEEG + HRV maneuvers) *(day 1, 7, wk 3 only)	30 min*	~1:20
9HPT	10 min	~1:20 (1:50*)
MN / PQ tests	8 min	~1:30 (2 hr*)
SRT / CRT	8 min	~1:38 (2:08*)
Stroop test	8 min	~1:46 (2:16*)
(3) n-back test	8 min	~1:54 (2:24*)
HRV daily	8 min	~2:02 (2:32)*
UPDRS-3	10 min	~2:10 (2:40*)

Abbreviations:
levodopa (L-DA),
dopamine agonist (DA),
Timed Up & Go (TUG),
9-hole pegboard test
(9HPT), simple / complex
reaction times (SRT/CRT),
heart rate variability (HRV)

1:30 - 1:45 total + 30-60 min
(breakfast) → up to 3 hr total
time from last dose

Note: The times listed on the chart are the target timepoints, and while every effort will be made to keep testing as close to the target time as possible, it is expected that there will be some variation in actual testing times. Times will be recorded. Variation in testing times is expected and will not be considered a protocol deviation. Home dose of dopaminergic medications will be given in the morning of the testing in the fasted state approximately 30 minutes prior to breakfast, allowing for at least 1 hour after dose prior to the start of testing to decrease variability in absorption.

Mobility assessment: Timed Up & Go (TUG) test

Abbreviated Title: Tolerability and efficacy of ketogenic diet in Parkinson's Disease

Version Date: 04/19/2021

To test the hypothesis of improvement occurring acutely (within days of reaching ketosis) due to improved mitochondrial function and neurotransmitter signaling, TUG will be tested by AI between group mean difference on study day 7 to target TUG power analysis (see section 9 for details). Pre-intervention screening visit time ≥ 11.5 s or < 11.5 s will be used as covariate for group randomization. Power analysis was chosen for TUG as a measure showing good intra-rater reliability (Dal Bello-Haas et al, 2011) and correlated with fall risk (Nocera et al 2013), hence meaningful for motor function. TUG will be done in the hallway of 7SW Neuro testing with distance of 10 ft demarcated by tape, using chair and stopwatch, best of three trials, daily as per table 2 testing schedule above. To control for biological / Levodopa variability, all secondary/exploratory tests will be done at approximately the same time with respect to dopaminergic Parkinson medication and other psychotropic medication dose and at approximate same time of day and same order of tests. Additionally, plasma levodopa will be measured twice daily at the times defined for BOHB blood draw.

[figure not shown]

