that certain medications, medication dosages, or DBS status will interact with dietary composition, either ketogenic or standard at standard protein intake. Study raters will remain blinded to diet group, because randomization scheme will be kept only by biostatistician and intervention status will be known otherwise only by nutrition staff, none of whom are involved in study rating. A possible exception is unblinding due to serious adverse event determined by study PI (non-rater) in consultation with safety monitor in which participant continues in the study, in which case data will be demarcated and not included in statistical analysis. Prior to admission, participants will be instructed to complete a log for 1 week of activities and diet at home. Upon admission to the Metabolic Unit and during hospital day 1, they will continue a regular, healthy hospital diet (carbohydrate predominant) and undergo baseline testing in mobility, physiologic and cognitive measures as per Section 3, Objectives and Endpoints). On hospital days 2-7, they will begin one of two diets: diet A, MCT-KD, according to set macronutrient ratios by daily energy: lipid 80% (25% of which is MCT oil), carb 5-10%, protein 10-15%, expected to be better tolerated than traditional NK, vs. diet B, standard American diet, lipid 30-35%, carb 55%, protein 10-15%. The goal is study time series of betaOHB, respiratory quotient, and continuous glucose ketosis measurements with tests of symptomatic impairment, with the hypothesis that nutritional ketosis augments mitochondrial function within hours of keto-induction and provides further benefit over days due to better functional neurotransmitter supply to key motor and cognitive synapses, aside from any long-term disease modification. Added benefits of an inpatient trial include monitored adherence and a look at biomarkers such as respiratory quotient in the metabolic chamber (CO₂:O₂ expected to go down due to diet), as well as easier access to daily repeated testing such as cognitive focused testing on executive function, memory and learning, as well as quantitative motor assessment of bradykinesia (keyboard, 9-hole pegboard), blinded UPDRS, and pain / fatigue assessment by subjective report.

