Based on the literature of ketogenic diet pilot studies (of 3 months duration or less) that no major adverse event was reported in three ketogenic studies in PD and another three in AD, it is unlikely that a serious adverse event (SAE) related to the intervention will occur. Monitoring will occur by daily clinical assessment (AI / metabolic unit staff) and electrolyte testing.

If there is a major adverse event, including but not limited to: Na <135, K < 3.4, Mag <1.0, HCO₃ < 22, and/or vomiting, study investigators including PI will be immediately made aware by Metabolic Unit staff, discussion will occur with the Independent Medical Monitor within 24 hours as to recommendations for therapy, and participant will be withdrawn from the study and study investigators unblinded to the participant's intervention status unless there is consensus by the IMM and Metabolic Unit staff that ketogenic diet can be continued with other measures taken (e.g. fluid rehydration, anti-nausea medication) or participation continued on a modified / less stringent ketogenic diet.

Despite double-blind design, unblinding may occur inadvertently. The participants will be instructed beforehand to make no mention of their diet, same as Metabolic Unit nurses and dieticians. If however unblinding of study rater(s) does unexpectedly occur, participants will by default remain in the study but be discounted from study power calculation and marked separately for statistical analyses.

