8.2.4.3 Genetic counseling - Not applicable

8.3 SAFETY AND OTHER ASSESSMENTS

- Biological specimen collection and laboratory evaluations.
For metabolic analysis, blood samples will be drawn at screening visit (basic metabolic panel), baseline (admission pre-intervention) and at discharge (admission post-intervention), as per Section. Additionally, blood will be drawn for beta-OHB levels at defined intervals (see Section 1.3 Schedule of Activities for details)
- Special assays or procedures required - continuous glucose monitoring
- No storage of specimen required. The data will be downloaded from the sensor attached to skin of the back of the upper arm to the Reader twice, on admission and on discharge.
- Heart rate variability monitor
- No storage of specimen involved. Data will be stored on a central application
- Counseling procedures, including any dietary or activity considerations
Counseling will occur at study debriefing visit on day of discharge or as otherwise arranged, and may also occur at any point during the one-week admission (Visit #2) or during the screening visit (#1). Counseling will be primarily focused on healthy diet, including low glycemic index, DASH diet, and Mediterranean diet as per USDA guidelines, and will emphasize that ketogenic diet remains a matter of research interest regarding previously found / putative benefits for Parkinson's Disease, however is congruent with aspects that are recommended by dietitians and physicians, such as minimizing salt and high glycemic index refined carbohydrates.
- Assessment of study intervention adherence - see Study Intervention Compliance, section 6.4
Administration of questionnaires or other instruments
At screening visit (#1), participant will be asked to fill out PDQ39, and UPDRS (Parts 1, 2 and 4) and NMSS will be administered by PI. On the day of discharge, UPDRS and NMSS will be repeated.
- Assessment of adverse events.

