There will be daily monitoring performed by metabolic unit staff and communicated to PI if concern, in turn discussing with independent medical monitor (IMM) and possibly unblinding AI if additional care required such as stopping the intervention, transfer to ICU. There will be no modification to the diets as outlined, to facilitate maintaining blinding and primary and secondary objectives of feasibility and ketosis ascertainment, respectively. There will be weekly meetings by investigators if any adverse events occurred as per Policy 801 (Refer to Section 8.4 for descriptions).

Abbreviated Title: Tolerability and efficacy of ketogenic diet in Parkinson's Disease

Version Date: 04/19/2021

Intervention side effects will be identified by the study LIP who is monitoring the patient during the admission and has daily contact with the participant. With blood glucose monitoring during the study, the nurses will contact study investigators for blood glucose value < 70 mg/dL. The hospital protocols are triggered for BG <40mg/dL that involve sending sample to NIH CC lab, including contacting study investigators for emergent care. For blood glucose 40-70, there will be the following procedure: if asymptomatic and fully alert, 1 cup juice / crackers, recheck in 30 minutes, repeat as necessary. If symptomatic (such as light-headedness, headache, nausea) / mental status lethargy, provide juice / crackers and contact study investigators for possible IV D50 administration.

The literature on safety of the ketogenic diet in adults in clinical trials is robust, including several trials in Parkinson's disease (Krikorian et al 2019, Phillips et al 2018, Vanitallie et al 2005) . The majority of these trials were conducted in the outpatient setting and adverse events were quite rare and typically minor in severity. Similarly, MCT powder/oil as a supplement to accelerate ketogenesis is reported to be safe in Alzheimer's Disease patients (Reger et al, 2004) as well as healthy volunteers (Harvey et al, 2018). Participants will be provided with contact information for the study team and asked to report any concerns, problems or new symptoms. During the 2-week outpatient phase, telephone monitoring may also occur as needed.

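### The associate-investigator role that times the TUG is also assigned the daily side-effect assessment, which conflicts with the plan's own shielding of raters and puts the blind at risk

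*Combined protocol and SAP*

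**What the plan says.** **Rating.** Section 4.1 states "All testing to be done by AI, at a certain scheduled time daily" and, for mobility, "TUG will be tested by AI between group mean difference on study day 7". It also says that one rater, the AI, takes most of the measurements. TUG is timed by stopwatch, best of three trials. An outside specialist also rates UPDRS part III from video; TUG has no second rater.

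**Safety duties.** Section 8.4.3.1 says "daily clinical assessment for volume status will occur by metabolic unit staff and AI with maintaining blinding as possible", and the sentence goes on to limit this to the case where no adverse event has occurred. Section 6.3 says "Monitoring will occur by daily clinical assessment (AI / metabolic unit staff) and electrolyte testing". Section 6.3 also has study investigators, the PI among them, told at once of low sodium, potassium, magnesium or bicarbonate, or of vomiting. Section 8.3 says "the nurses will contact study investigators for blood glucose value < 70 mg/dL".

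**Safeguards.** Under Section 8.4.3.1, vomiting and keto-induction symptoms are reported to unit staff and "relayed to study PI (not involved in rating) and independent medical monitor (IMM"). Section 8.4.4 asks that non-serious, non-emergent events be raised first with the PI or IMM, expressly to protect the raters' blind, and brings the AI into non-emergent evaluation only after study completion. Section 6.3 withholds allocation from investigators and raters until measurements end.

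**The PI.** Section 6.1.1 refers to "unblinding due to serious adverse event determined by study PI (non-rater"). For the screening visit, Section 8.3 says "UPDRS (Parts 1, 2 and 4) and NMSS will be administered by PI". Its next sentence has UPDRS and NMSS repeated on the day of discharge and names nobody to do it.

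**The concern.** The daily assessment looks for what the plan expects from one arm: Section 8.4.3.1 lists dehydration, electrolyte depletion, acidosis and vomiting as risks of the ketogenic diet. A clinician who checks for these each day may form a view of the arm and then time that participant's walk. A TUG time depends partly on instruction, encouragement and stopwatch handling, so an expectation could enter the result and look like a diet effect.

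The stake is the day-7 between-group TUG difference. It sets the sample size (Section 9.2) and drives the interim efficacy boundary (Section 9.4.6). The plan describes no check of what the rater believes. Its comfort about blinding in Section 6.3 concerns participants' guesses in another study.

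**Working it through.** No figure in the plan is disputed, so the main check sets the sections side by side.

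**Step 1: what could reach the rater, and by which route.**

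| Information | Route that shields the rater | Route that may reach the rater |
|---|---|---|
| Volume status | Blinding kept where possible (8.4.3.1) | AI assesses daily (8.4.3.1; daily clinical assessment in 6.3) |
| Vomiting | Unit staff to PI and IMM (8.4.3.1) | Study investigators told at once (6.3) |
| Abnormal electrolytes or bicarbonate | None stated | Study investigators told at once (6.3) |
| Glucose below 70 mg/dL | None stated | Study investigators called (8.3) |
| Non-serious events raised by the participant | PI or IMM first; AI after study completion (8.4.4) | AI's daily clinical assessment (6.3) |

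The alerts do not name the rater, but nothing excludes the rater. The paragraph on relationship to the intervention, in Section 8.4.3, also has causality judged by the investigator who examines the participant. If that is the AI, the rater may be asked whether the diet caused an event.

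**Step 2: is it the same AI?** AI means associate investigator, and several people hold the role: nutrition staff (6.4), an unblinded investigator who generates study numbers (8.2.4.1), and one who has Parkinson's disease (5.6). But the AI in Section 8.4.3.1 is someone whose blind is to be preserved, and Section 8.3 speaks of possibly unblinding the AI if more care is needed. The nutrition and study-number AIs already know diet or allocation, so neither fits. A blinded AI in daily contact with participants fits the rater. Identity is likely but not stated, and nothing separates the two functions.

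**Step 3: what arithmetic is available.** Section 9.2 gives a difference of 4.5 s, SD 4 s and significance level 0.0492.

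- Effect size: d = 4.5/4 = 1.125.
- Power comes from the noncentral t with 2n − 2 degrees of freedom and noncentrality d√(n/2).
- n = 14 per group: 26 degrees of freedom, noncentrality 1.125 × √7 = 2.98, critical value 2.063, power 81.5%.
- n = 13 per group: power 78.4%. So 14 is the smallest n reaching 80%, as the plan says.
- Dropout: 28/(1 − 0.10) = 31.1, recruited as 32 (16 per group). The plan's figure reproduces.

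The bias itself cannot be calculated: the documents give neither a rate of correct inference nor the effect of expectation on TUG. One knock-on effect can be shown. Section 6.3 removes participants whose rater is unblinded from the power calculation and marks them separately. If recognised unblinding left fewer than 14 per group, power at the same d and significance level would be 74.7% with 12, 66.0% with 10 and 55.0% with 8. These counts are assumed scenarios. They cover recognised unblinding only, not quiet inference from signs.

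**The case against.** The strongest reply is that the blind is intact. The biostatistician and nutrition staff hold the allocation, the AI is blind by default, symptom reports go first to the PI and IMM, and known unblinding of a rater is handled in Section 6.3. Section 8.3 gives identification of side effects to a study LIP rather than to the rater. TUG is secondary in a feasibility pilot and is standardised: a taped 10 ft course, a fixed test order and best of three.

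Much of this stands. A reader might infer that assigned duties break the blind; the documents do not show that. They show a route to inference, with an intention to contain it. But concealing the list does not prevent inference from signs, the Section 6.3 provision acts only on unblinding that someone recognises, and nothing says that the LIP is a different person from the AI. Standardisation narrows the room for rater influence without closing it.

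A reader might also turn the GI event rates in Section 2.3.1 (49% with an MCT product, 27% with placebo) into a rate of correct guesses. That is not supported. The rates come from an Alzheimer's disease study of a proprietary powder, and Section 2.3.1 says GI effects fell substantially once it was given in a meal-replacement drink. The step would also assume that the rater learns of every GI event, whereas the duty in Section 8.4.3.1 is volume status and GI reports are routed elsewhere. Section 8.4.3.1 itself says that frequencies of the diet-related events are not defined.

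**Conclusion.** The conflict is real: Sections 6.3 and 8.4.3.1 give the rating role a daily safety assessment, and Sections 6.3 and 8.3 leave it open to alerts, while Sections 8.4.3.1 and 8.4.4 try to keep such information from raters. The consequence is a risk of functional unblinding for the powered TUG comparison, of unknown size. This rests on the assessing AI being the rating AI, which the wording makes likely but does not state. It should be fixed because the remedy costs little, not because bias has been demonstrated.

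A reader might further infer that the PI, who receives side-effect reports, scores NMSS and UPDRS parts 1, 2 and 4 after the diet has begun. Section 8.3 names the PI only at screening, before any diet. Sections 1.3 and 4.1 put the post-intervention assessment at week 3, when both groups are on the ketogenic diet, although knowledge of the inpatient allocation could still matter. These outcomes are exploratory. What remains is a minor reconciliation: a PI labelled a non-rater is assigned a rating, and the repeat is at discharge in one section and at week 3 in others.

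**What to change.** In Sections 6.3, 8.3 and 8.4.3.1, state that the AI who rates TUG and the other tests does not perform the daily volume and side-effect assessment. State also that this AI does not receive electrolyte, glucose, beta-hydroxybutyrate, GI-diary or keto-induction results until that participant's last rating, except in an emergency. Direct these duties and alerts to the Metabolic Unit staff, the non-rating PI and the IMM. Thresholds, responses and all other clinical rules stay as they are.

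The cost is a text edit and a reassignment among people already named. The testing AI is no longer available for routine daily safety review, so the PI and unit staff carry slightly more of it.

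Separately, name who administers NMSS and UPDRS parts 1, 2 and 4 at each visit, and reconcile Section 8.3 with the non-rater label in Sections 6.1.1 and 8.4.3.1 and with the week-3 timing in Sections 1.3 and 4.1. Do not move these symptom interviews to the TUG rater ahead of any TUG rating, because that would add the exposure the change is meant to remove.
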